12.2 Methods of statistical analyses

12.2.1 General principles

No formal statistical hypothesis testing will be performed in this study. Data will be presented by actual dose received.

12.2.2 Patient characteristics

The following demographic variables will be summarized: age, sex, race, height, weight and BMI for all dose groups as appropriate.

Medical/surgical histories and medications taken before screening will be listed including comments and coded fields.

Baseline assessments of safety variables (ECG, vital signs, and laboratory parameters) will be listed by dose groups as appropriate.

12.2.3 Safety and tolerability

All safety and tolerability data will be listed as specified in the SAP.

Adverse events will be collected for each patient from visit 1 until follow-up. Serious adverse events will be recorded from the time when informed consent is obtained (Visit 1) until the follow-up visit.

The following summaries of AEs will be given by treatment and in total:

The number of patients who had any AEs, SAEs, AEs that led to withdrawal, AEs related to study drug and AEs with severe intensity.

If the number of AEs is sufficiently large, summaries will be presented by PT (Preferred term) and SOC (System organ class) according to MedDRA vocabulary.

Severity, time of onset, duration, action taken, concomitant therapy started and patient outcome of the AEs will be given in data listings only. AEs which were reason for premature discontinuation of study drug will be listed separately.

Furthermore, SAEs and AEs that led to withdrawal will be listed separately.

12.2.4 Efficacy on DSA, CDC CXM and FACS CXM

CDC crossmatch results (positive or negative and when applicable titer) before and after IdeS treatment will be determined for each patient and presented in listing sorted by treatment, patient, and time-point. In addition, time to conversion of crossmatch will be calculated.

FACS crossmatch results (positive or negative and when applicable channel shift) before and after IdeS treatment will be determined for each patient and presented in listing sorted by treatment, patient, and time-point. In addition, time to conversion of crossmatch will be calculated.

HLA antibodies including DSA will be measured with SAB assays. Summary statistics of MFI values for DSA and for all HLA for each patient will be produced by time point, including min, 10th percentile, median, 90th percentile, and max. In addition, patient listings of MFI values for DSA and all HLA for all patients will be produced.

12.2.5 Pharmacokinetics

Pharmacokinetic (PK) variables will be summarized using appropriate descriptive statistics (e.g. n, geometric mean, harmonic mean for $t_{1/2}$, coefficient of variance (CV), min, median, max) by treatment group.

12.2.6 Pharmacodynamics

All data associated with the efficacy of IdeS in cleaving IgG will be presented using listings for each dose group. If feasible, the data will be explored graphically.

12.2.7 Anti-drug antibodies

All anti-IdeS antibody data will be presented using listings.

12.3 Determination of sample size

Sample size is not based on formal statistical considerations. Due to the nature of the primary endpoint of the study it is expected that data from 15-20 patients should suffice to achieve the objectives of the study. Also, the sample size is in line with experience from previous similar Phase II studies with other compounds to obtain adequate safety, tolerability and PK data to achieve the objectives of the study.

13 Publication policy

13.1 Clinical Study Report

The results from this study will be reported in a clinical study report (CSR) within one year after completion of the last patient. This will be prepared by Hansa Medical AB and submitted for comments and signature to the signatory investigator(s).

13.2 Confidentiality and Ownership of data

Any confidential information relating to the IMP or the study, including any data and results from the study will be the exclusive property of Hansa Medical AB. The investigator and any other persons involved in the trial will protect the confidentiality of the proprietary information belonging to Hansa Medical AB.

13.3 Publication and Public Disclosure

13.3.1 Publication Policy

At the end of the study, one or more manuscripts for joint publication may be prepared in collaboration between the investigator(s) offered authorship and Hansa Medical AB.

Any external Contract Research Organisation or laboratory involved in the conduct of this study has no publication rights regarding the study.

## List of abbreviations and definition of terms

ADA	Anti-drug antibody
ADaM	Analysis data model
AE	Adverse event
AUC	Area under the concentration versus time curve
BMI	Body mass index
BP	Blood pressure
CDC	Complement dependent cytotoxicity
C max	Maximum observed concentration
CRF	Case report form
CV	Coefficient of variation
DSA	Donor specific antibodies, anti-human leukocyte antigen (HLA) donor-specific antibodies
ECG	Electrocardiogram
FACS	Fluorescence-activated cell sorting
IMP	Investigational medicinal product
LD	Living donor
LLOQ	Lower limit of quantification
MedDRA	Medical Dictionary for Regulatory Activities
NCA	Non compartmental analysis
PD	Pharmacodynamics
PK	Pharmacokinetics
PP	Per-protocol analysis set
PRA	Panel reactive antibody
PT	Preferred term
SAB-HLA	Single antigen beads - human leukocyte antigen
SAE	Serious adverse event
SAP	Statistical analysis plan
SAS	Safety analysis set
SD	Standard deviation
SE	Standard error
SOC	System organ class
SDDM	Study data tabulation model
T ½	Elimination half-life
TEAE	Treatment emergent adverse event
TLF	Tables, listings and figures
T max	Time of observed C max

## 1 Introduction

This document describes the planned statistical analyses for study 15-HmedIdeS-06 which will include data processing, data analyses and data presentation. This SAP is based on the protocol version 5.0 applicable for USA dated 20 March 2017, version 6.1 applicable for Sweden dated 14 June 2017, and version 7.2 applicable for France dated 13 September 2017. The differences between the country specific protocol versions only relate to inclusion criteria and will not influence the presentation of data.

The original planned collection of data was later extended by amendment 7, dated 8 December 2017. An additional CRF was designed to include donor characterisation, recipients' previous transplantation history and transplantation outcome.

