2.6 Risk/benefit and ethical assessment

Patients included in this study have both a wide breadth of sensitization and high reactivity to common HLA antigens. Transplantation is not possible using current standards for desensitization due to antibodies creating a positive crossmatch test. These patients are so strongly sensitized that even with paired donation it is highly unlikely to identify a donor with a genotype that would allow desensitization with a reasonable likelihood of success. In addition, some of the patients will have failed on earlier attempts of desensitization. Eligible patients will either be on the waitlist for a deceased allograft or have an identified live donor. However, in both groups transplantation is not indicated due to antibodies creating a positive crossmatch test. Sensitized patients have an increased risk of ABMR associated with negative long-term graft outcome. From previous studies it is known that the ABMR frequency in the highly sensitized patient population is between 25-39% after desensitization (Abu Jawdeh, Cuffy et al. 2014). There are currently no approved treatments for ABMR but in the event of ABMR the patient will be treated according to best clinical practice. This may include plasmapheresis, IVIg, complement inhibitors and anti-CD20 antibodies. The risk for ABMR and graft loss should be weighed against the morbidities, low quality of life and increased mortality associated with long term dialysis. Data demonstrate that transplantation following desensitization is clearly associated with short- and long-term survival benefits compared to staying in dialysis (Montgomery, Lonze et al. 2011, Vo, Petrozzino et al. 2013, Orandi, Garonzik-Wang et al. 2014, Orandi, Luo et al. 2016). In addition, the patient's quality of life is dramatically increased after successful transplantation and there are substantial cost-savings associated with desensitization and subsequent transplantation compared to long-term dialysis (Vo, Petrozzino et al. 2013).

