**The secondary objectives of this study are:**

- To determine DSA levels at multiple times (pre-dose, 2, 6, 24 and 48 hours and days 7, 14, 21, 28, 64, 90, 120 and 180) post imlifidase treatment
- To determine time to creating a negative CDC crossmatch test
- To determine time to creating a negative FACS crossmatch test
- To evaluate safety parameters (adverse events, clinical laboratory tests, vital signs and ECGs) following imlifidase treatment up to day 180
- To monitor kidney function after imlifidase treatment as assessed by, filtration (eGFR), creatinine and proteinuria
- To establish the PK profile of imlifidase
- To establish the PD profile of imlifidase (cleavage and recovery of IgG)
- To establish the immunogenicity profile of imlifidase (ADA)

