### 4.3 Demographics and other baseline characteristics

The following demographic and body measurements variables will be summarised: age, sex, race, height, weight and BMI.

Medical and surgical history and concomitant illness will be summarised by MedDRA system organ class (SOC) and preferred term (PT) version 18.1. Prior and concomitant medication will be tabulated by WHO drug version 153E, level 4 (chemical/therapeutic/pharmacological subgroup) and level 5 (Chemical substance). Medication is categorised as “Started prior to study start” and “Ongoing” in the eCRF and these responses will be used to categorise as prior and concomitant respectively. Medication was recorded in the original eCRF. The additional data recording collected specifically medication for de-sensitization and rejection. There may therefore be an overlap with prior and concomitant medication and the de-sensitization and rejection medication will be tabulated separately.

Previous kidney transplant history will be summary tabulated.

Baseline assessments of ECG, physical examination, vital signs, body measurements and laboratory parameters will be presented as part of the general tables and listings for these parameters.

ImmunoCAP IgE (ADA) is recorded at baseline only and will be listed. Serology and sperm sample will be listed.

The drug exposure will be listed showing number of doses, planned dose and actual dose per kg BW.

Donor characteristics will be listed.

Recipient and donor HLA types will be listed.

Recipient and donor blood groups will be listed.

Deceased donor characteristics will be listed.

Protocol deviations will be listed.

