### 4.5.1 Adverse events

Adverse events (AEs) will be classified according to the Medical Dictionary for Regulatory Activities (MedDRA) version 18.1.

A treatment emergent adverse event (TEAE) is any AE occurring after the administration of the IMP and within the time of the residual effect period or a pre-treatment AE or pre-existing medical condition that worsens in intensity after administration of the IMP and within the time of the follow up period. Based on the half-life and the PD properties of imlifidase the residual drug effect is considered 30 days after administration.

An AE overview summary table will be prepared including the number of patients reporting an AE, the percentage of patients (%) with an AE, and the number of events (E) reported for the following categories:

- TEAEs
- Related TEAEs
- Serious TEAEs (SAEs)
- TEAEs leading to withdrawal
- Deaths

Treatment-emergent AEs will be summarised in a table by dictionary level, i.e., SOC and PT for MedDRA. The table will display the total number of patients reporting an AE, the percentage of patients (%) with an AE and the number of events (E) reported. AEs will be presented by SOC and PT sorted in decreasing frequency of occurrence.

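### The SAP's undeclared 30-day limit moves later new-onset AEs out of the TEAE tables, against the protocol and the day-180 safety objective, and the SAP text names no summary of transplantation outcome

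*SAP*

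**What the plan says.** **Outcome data.** SAP section 1 reports that amendment 7 brought an extra CRF for donor data and for recipients' previous "transplantation history and transplantation outcome". SAP 4.3 then gives two of these three items an output: "Previous kidney transplant history will be summary tabulated" and "Donor characteristics will be listed". It adds that "the de-sensitization and rejection medication will be tabulated separately". The third item, outcome, is not mentioned again. SAP 4.6, on other endpoints, is marked as not applicable. SAP 4.1 says in general that all data are listed.

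**TEAE window.** SAP 4.5.1 has two limbs. A new AE is treatment-emergent if it falls within the residual effect period, and "the residual drug effect is considered 30 days after administration". A pre-treatment AE or an existing condition that gets worse is treatment-emergent if this happens at any time in follow-up. Protocol 6.3.1 has the same two limbs but uses the follow-up period for both.

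**Safety objective.** SAP 1.1.1: "To evaluate safety parameters (adverse events, clinical laboratory tests, vital signs and ECGs) following imlifidase treatment up to day 180".

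**AE outputs.** The overview table in SAP 4.5.1 treats SAEs as serious TEAEs and has a Deaths row with no stated window. The list of summary tables that follows has four entries for TEAEs and two for SAEs, and the SAE entries carry no TEAE label. Post-treatment AEs appear only among the listings. SAP section 5 declares one deviation from the protocol analysis: who performs the PK analysis.

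**The concern.** The protocol's benefit-risk argument (2.6) sets the risk of antibody-mediated rejection (ABMR) and graft loss against long-term dialysis, and gives the background rate: "ABMR frequency in the highly sensitized patient population is between 25-39% after desensitization". It also names infection as a risk of removing IgG. Protocol 4.2 lets the DSMB recommend stopping for graft losses, and both documents keep patients who lose a graft in follow-up. These are therefore events on which the safety conclusion will turn.

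Under the SAP as written, a first rejection, a graft loss or an infection with onset on day 60 is not a TEAE. It would be missing from the tables of all TEAEs, TEAEs by causality and TEAEs by intensity, and no outcome summary is named that would catch the rejection or the graft loss. A reader of the summary tables could take a 30-day picture for a 180-day one. Because section 5 is silent, nothing would signal that the definition had changed.

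**Working it through.** The plan states no figure on this point that could be reproduced. The check compares the texts and counts days.

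**Step 1: trace each data type added by amendment 7 (SAP section 1) to its output.**

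| Data type | Planned output |
|---|---|
| Donor characterisation | Listed (SAP 4.3) |
| Previous transplantation history | Summary table (SAP 4.3) |
| Desensitization and rejection medication | Separate tabulation (SAP 4.3) |
| Transplantation outcome | None named; only the general listing rule (SAP 4.1) |

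Related outputs exist. SAP 4.5.2 tabulates eGFR, creatinine, proteinuria and the day-180 biopsy by time point. None of these counts graft losses or rejection episodes, or gives their timing. Protocol 6.6.6 also collects reports of biopsies done for cause, and the SAP names no summary of them.

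**Step 2: compare the TEAE definitions.**

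| Limb | Protocol 6.3.1 | SAP 4.5.1 |
|---|---|---|
| New-onset AE | To the end of follow-up | 30 days after administration |
| Worsening of an earlier AE or condition | To the end of follow-up | To the end of follow-up |

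Only the new-onset limb differs. Protocol 12.2.3 promises counts of patients with any AE and with SAEs, and sets no 30-day limit.

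**Step 3: size of the gap.** Inputs: follow-up to day 180 with a last-visit window of ±14 days (flow chart), a window of 30 days (SAP 4.5.1), and a second dose within 2 days of the first (SAP section 2), used in 3 patients (SAP 4.1).

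Share outside = (last day − end of window) / last day.

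- One dose, last visit on day 180: (180 − 30)/180 = 150/180 = 83.3%.
- Last visit on day 166: 136/166 = 81.9%. Last visit on day 194: 164/194 = 84.5%.
- Second dose on day 2, if the 30 days run from that dose: (180 − 32)/180 = 148/180 = 82.2%.

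Visits 9 to 12 (days 64, 90, 120 and 180) lie wholly after the window. They are four of the eleven visits, 2 to 12, at which the flow chart schedules AE assessment. Under the protocol definition the new-onset window is 180/30 = 6 times as long.

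**Step 4: do the SAE tables close the gap?** The two SAE entries in the list of summary tables have no TEAE label, which suggests all SAEs. The overview equates SAEs with serious TEAEs, which suggests the 30-day window. The text supports both readings. Even on the wider one, counts by system organ class and preferred term give no day of graft loss and no transplanted-patient denominator.

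**The case against.** The case for leaving the plan alone has real content.

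- **Late events are not all excluded.** A reader might infer that everything from day 31 to day 180 drops out of every TEAE table. That is too strong. The worsening limb runs through follow-up, and two-dose patients may be covered to about day 32. This stands, although a first rejection or the loss of a new graft does not fit the worsening limb naturally.
- **Late serious events may be tabulated.** Many graft losses and rejections would meet the SAE criteria in Protocol 6.3.2, and the SAE tables and Deaths row state no 30-day limit. This also stands: the documents do not show that such events go uncounted. They leave the matter open, and that needs settling.
- **Some outcome-related data are summarised.** Rejection medication, renal function and the day-180 biopsy are tabulated, and all data are listed.
- **Graft survival and rejection are not endpoints.** The study is exploratory and descriptive, so Kaplan-Meier curves, confidence intervals and splits by donor type are a matter of preference. Agreed. The day-180 safety objective and the collection of outcome data still call for a plain count.
- **Amendment 7 and the table shells are not available here.** The shells may hold an outcome table. SAP section 8, however, calls the templates working documents that can change after signature, so they do not replace a statement in the SAP. That the outcome form records graft loss and rejection is a reasonable inference; SAP section 1 speaks only of outcome.

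**Conclusion.** The point holds in this form: the SAP shortens the new-onset TEAE window from the whole of follow-up to 30 days, against the protocol definition and the day-180 objective, without declaring it; and the SAP text names no summary of transplantation outcome. This should be corrected.

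The size is 150 of 180 days, or 83% (82% to 85% across the last-visit window and a second dose). This is a share of calendar time and says nothing about the share of events.

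A reader might go further and apply the protocol's 25-39% ABMR rate to 15-20 patients, giving 0.25 × 15 = 3.75 to 0.39 × 20 = 7.8 cases, and treat these as cases the tables would miss. The documents do not support that. The rate carries no timing, the product assumes that every patient is transplanted although both documents provide for patients who are not, and the number starting after day 30 could be zero.

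The conclusion rests on two assumptions: that AEs outside the TEAE window are what the SAP means by post-treatment AEs, which it does not define; and that the TEAE definition is the same in the protocol versions on which the SAP is based. SAP section 1 supports the second, since it says those versions differ only in inclusion criteria.

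**What to change.** 1. In SAP 4.5.1, either restore the protocol's TEAE window so that new-onset events count to day 180, or keep the 30-day window, add AE and SAE summary tables for day 31 to day 180, and declare the change in section 5. If the 30-day window stays, state which dose it runs from when two are given.
2. State that the SAE tables and the Deaths row cover all events to day 180, and align the wording of the overview with this.
3. Add to SAP 4.5 one descriptive day-180 table on the safety set, using the data collected: number transplanted, deaths, and graft losses and rejection episodes with day of onset. Kaplan-Meier estimates, exact confidence intervals and a split by donor type are optional; they are descriptive and would not conflict with the rule against formal testing.

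The third item alone is not enough: late new-onset events other than transplant outcomes, such as infections, would stay outside the TEAE tables. The cost is a few extra descriptive tables. How finely rejection can be classified depends on what the amendment 7 form recorded, which should be checked first.

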### 1.1 Study objectives and endpoints

#### 1.1.1 Objectives

**The primary objective of this study is:**

- To assess the imlifidase efficacy in creating a negative crossmatch test

**The secondary objectives of this study are:**

- To determine DSA levels at multiple times (pre-dose, 2, 6, 24 and 48 hours and days 7, 14, 21, 28, 64, 90, 120 and 180) post imlifidase treatment
- To determine time to creating a negative CDC crossmatch test
- To determine time to creating a negative FACS crossmatch test
- To evaluate safety parameters (adverse events, clinical laboratory tests, vital signs and ECGs) following imlifidase treatment up to day 180
- To monitor kidney function after imlifidase treatment as assessed by, filtration (eGFR), creatinine and proteinuria
- To establish the PK profile of imlifidase
- To establish the PD profile of imlifidase (cleavage and recovery of IgG)
- To establish the immunogenicity profile of imlifidase (ADA)

#### 1.1.2 Endpoints

**The primary endpoint of this study is:**

- Efficacy defined as imlifidase ability to create a negative crossmatch test within 24 hours after imlifidase dosing

**The secondary endpoints of this study are:**

- DSA levels at pre-dose and 2, 6, 24 and 48 hours and days 7, 14, 21, 28, 64, 90, 120 and 180 post imlifidase treatment

[figure not shown]
- Time to creating a negative CDC crossmatch test
- Time to creating a negative FACS crossmatch test
- Safety parameters (adverse events, clinical laboratory tests, vital signs and ECGs)
- Kidney function after imlifidase treatment assessed by, filtration (eGFR), creatinine and proteinuria up to 180 days post treatment
- PK profile of imlifidase up to day 14
- PD profile of imlifidase (cleavage and recovery of IgG) up to day 180 post imlifidase
- Immunogenicity profile of imlifidase by measuring ADA

## 2 Study design

This is a phase II, open label exploratory study to assess the imlifidase efficacy in creating a negative crossmatch test (CXM) in a total of 15-20 patients (7-13 with living donors and 7-13 with a deceased donor) who exhibit DSAs and have a positive crossmatch test to their available live donors. The first 3 patients in this study will receive a kidney from a deceased donor. The study will primarily examine the efficacy of imlifidase in creating a negative CXM in patients. Included patients will be treated with imlifidase on day 0. If it is considered safe and the desired effect is not achieved (negative crossmatch) a second dose can be given within 2 days of the first infusion. In addition to imlifidase patients will be given high dose IVIg (2 g/kg BW, maximum of 140 g) on day 7 and anti CD20 (Rituximab) on day 9 as outlined in [Figure 1](#). DSA levels will be monitored 2, 6, 24 and 48 hours and 7, 14, 21, 28, 64, 90, 120 and 180 days after the last imlifidase dosing. Safety, including kidney function will be monitored at multiple time points up to 180 days after treatment. PK, PD and ADA will be followed. For details on assessments see flow chart in [Table 1](#). Patients who are not eligible for transplantation after imlifidase treatment will not be transplanted and thus will not receive any induction therapy or immunosuppression. All patients who receive imlifidase will also be asked to remain in the study and be followed up according to the study protocol even if they are not transplanted. In addition, patients who lose their graft during the course of the study will remain in the study and be followed up according to the study protocol and clinical practice at the respective site.

